8. RESEARCH QUESTION AND OBJECTIVES

8.1 RESEARCH QUESTION

Research question:

The study's overall research question and objective is to characterize patients who are prescribed Intuniv[®], to describe prescribing patterns among physicians and to evaluate if additional risk minimisation measures that had been provided to physicians were successfully implemented and effective. Data on use of Intuniv[®] will be provided on an annual basis for up to 5 years in up to 10 European countries. In Belgium, Finland, Ireland, and Netherlands, data on the use of Intuniv[®] will be collected within a prescriber survey which is described in this protocol. In other countries a database analysis will be performed which is described in a separate protocol (Protocol data base study).

8.2 OBJECTIVES

Primary objectives:

- To characterize patients who are prescribed Intuniv® with a specific focus on
 - o Indications other than ADHD
 - o Children less than 6 years of age
 - o Adults
 - O Patients who did not have any first-line stimulant treatment prior to their first prescription of Intuniv®
 - o Prescribed overdose of >7 mg/day, or of >4 mg/day for patients ≤12 years of age
- To describe prescribing patterns of Intuniv® among physicians

Secondary objective:

• To measure the effectiveness of the additional risk minimisation measure (educational materials for healthcare professionals) in order to assess compliance with the indication and with visits and measurements needed during the first year of treatment

9. RESEARCH METHODS

9.1 STUDY DESIGN

This is a multi-national, cross-sectional, non-interventional and anonymous web-based survey carried out among physicians. This approach was chosen as it will allow to collect all variables required, including data to assess compliance with the indication and with visits and measurements needed during the first year of treatment.

9.2 SETTING

The survey will be conducted among prescribers of Intuniv[®] in the selected countries (Belgium, Finland, Ireland, and Netherlands) and conducted annually from 2019 to 2022. In order to minimize selection bias, physicians will be randomly recruited using nationally representative external lists (OneKey lists). The prescriber sample selected will be described by specialty, graduation year, gender, and type of location (e.g. urban/rural). It is planned to collect data for 50 to 100 patients per country who have been prescribed Intuniv[®] at least once during the study period. Recruitment will occur from the total population of healthcare practitioner groups who are most likely to treat patients with ADHD. Physicians will be recruited as described in 9.5.1. The physicians who are eligible for participation will be instructed to select the patient record based on the last patient they have seen, for who at any time in the last 12 months (or, for the first report, since country specific launch) they have prescribed Intuniv[®] (whether or not Intuniv[®] was prescribed at that last visit). Recruitment of physicians will be done at random for each annual survey, with the aim to avoid having the same physicians in each survey. However, overlaps within the groups of physicians are still possible. The number of physicians per specialty who provided data for the survey will be included in the report. Information regarding the total population of physicians will also be included. One to 10 patients per physician may be reported, with the most recent patients being reported first.

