4.6 Variables

The collected information includes:

- Physician related data (demographics, setting, prescriber's specialty)
- Drug utilization data: indication of use/diagnosis, patient characteristics (age, gender, comorbidities), data on patterns of drug use (dosing, first time user, repeat user, duration, discontinuation of ADHD therapy and switches), frequency of monitoring and weight, blood pressure, heart rate if information is available.

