Stimulants have been available for decades in Europe. The first non-stimulant medication was approved in the United Kingdom in 2004, and in Germany in 2005. In 2009, Shire Pharmaceuticals has launched a novel non-stimulant drug in USA and Canada: extended-release guanfacine (Intuniv®). Intuniv® is a long-acting, once-daily formulation of guanfacine (a selective alpha-2A-adrenergic receptor agonist) indicated for treatment of ADHD in 6 to 17 year old children and adolescents. It is indicated as a second-line treatment for patients for whom stimulants are not suitable, not tolerated or have been shown to be ineffective. As listed in the SmPC, Intuniv is indicated for the treatment of ADHD in children and adolescents 6-17 years old for whom stimulants are not suitable, not tolerated or have been shown to be ineffective.

Intuniv[®] can be prescribed as monotherapy and as adjunctive therapy to stimulant medications. Intuniv[®] has demonstrated improvement of a range of ADHD symptoms that can

be disruptive, such as inattention, hyperactivity, impulsivity, and extensive loss of temper (12). Intuniv[®] is not a controlled substance, which sets it apart from most other ADHD drugs. The active compound of Intuniv[®], guanfacine, is also used for treatment of hypertension, but the marketing authorization does of Intuniv[®] does not include that indication. Therefore, use of Intuniv for treatment of hypertension would be considered off-label use. The effects of Intuniv[®] for treatment of ADHD have been demonstrated in controlled trials in children and adolescents and in adult healthy volunteers (1).

Background and rationale of the current study

Intuniv[®] has not been studied in children under age 6 years, adults and the elderly. Therefore, in order to avoid any potential or unknown risks, it is currently not indicated for use in these populations.

Furthermore, there are identified risks of bradycardia, syncope, hypotension/decreased blood pressure, withdrawal blood pressure increase, sedative events, and weight increase. In order to minimize these identified risks, careful assessment of patients' blood pressure, weight and heart rate is required before initiation and during treatment of a patient with Intuniv[®].

To increase awareness and knowledge on these requirements, Shire Pharmaceuticals has developed and distributed educational materials to potential prescribers of Intuniv[®].

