9.3 VARIABLES

The survey aims to characterize patients who are prescribed Intuniv[®] and describe prescribing patterns of Intuniv[®] among physicians in European countries.

The following information is planned to be collected in the survey:

- Physician related data
 - o demographics
 - o setting
 - o prescriber's specialty
- patient characteristics
 - o age
 - o gender
 - o co-morbidities
- indication of use (diagnosis) according to WHO ICD 10 classification
- data on patterns of drug use
 - o first time user
 - o repeat user
 - o duration of treatment
 - o discontinuation of ADHD therapy
 - o switches (both from Intuniv[®] to other ADHD medications and other ADHD medications to Intuniv[®])
 - o dosing/ overdose (defined as daily dose of >7 mg or of >4mg in patients ≤12 years of age)
- use of Intuniv[®] as second line treatment after psychostimulant prescription at any time prior to the patient's first prescription of Intuniv[®]
- frequency of monitoring (physician) visits during the first year of therapy
- weight, blood pressure and heart rate during Intuniv[®] exposure

A detailed description of all variables and definitions is provided in Table 3 of the SAP for the survey protocol.

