9.7.3 Questionnaire analysis

The reports will include descriptive statistics of all parameters analyzed. As part of this analysis, the description of missing data for each outcome of interest will be provided. Missing values are expected to be few and distributed at random. Since there is no applicable method unanimously accepted, there will be no replacement or imputation of missing data (17).

For continuous variables the number of non-missing observations, mean, standard deviation, median, minimum and maximum will be presented.

Categorical data will be summarized using frequency and percentage. 95% confidence interval may be constructed around the percentage values for some variables. Some of the variables may also be summarized by country.

The educational materials will be considered to be effective if at least 80% of physicians will have responded correctly to at least 75% of the questions in the survey in which knowledge on the educational material is assessed.

This hypothesis is based on empirical numbers.

Evaluation of the success rate will be based on the percentage of correct answers to questions A2 to A5 in Section 4 ("Awareness and knowledge of risk minimisation measures") of the survey questionnaire.

Two analyses to evaluate the effectiveness of the risk minimization measures will be performed:

In the main analysis all questionnaires will be evaluated. In the subgroup analysis, only questionnaires of the physicians who answered "Yes" to question A7 ("Did you receive educational material regarding Intuniv[®]?") will be included. The subanalysis will allow to evaluate if awareness of the educational material may affect the number of correct answers.

More detailed information regarding the evaluation of the effectiveness is given in the survey SAP.

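### Selecting the most recently seen patients ties selection to visit frequency, so first-year visit compliance is likely to be overstated wherever a physician reports only some eligible patients

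*Protocol*

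**What the plan says.** Section 9.2 of the protocol draws physicians at random from national lists, but not the patients within a physician. Physicians "will be instructed to select the patient record based on the last patient they have seen", among those prescribed the drug in the last 12 months (for the first report, since launch), "whether or not Intuniv[®] was prescribed at that last visit". The same section adds: "One to 10 patients per physician may be reported, with the most recent patients being reported first". Sections 4.5, 9.4 and 9.7.1 repeat the recency rule.

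The secondary objective in section 8.2 concerns "compliance with the indication and with visits and measurements needed during the first year of treatment". Section 9.3 lists "frequency of monitoring (physician) visits during the first year of therapy" as a variable.

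Section 9.5.1 plans 15 to 20 prescribers and 50 to 100 patients per country and year. Section 9.2 presents random recruitment of physicians as the safeguard against selection bias. Section 9.9 covers volunteer bias among physicians and the limits of web surveys. Neither section mentions how patients are chosen within a physician.

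**The concern.** A patient who attends often is more likely to be among the last few seen than one who attends rarely or has stopped attending. If the physician reports only some eligible patients, the sample is enriched for frequent attenders, and frequency of attendance is one of the things being measured.

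The patient records are the plan's evidence on what prescribers actually do about monitoring. The numerical effectiveness criterion in section 9.7.3 tests physicians' knowledge only. An upward shift in visit compliance would make monitoring look better than it is. Collecting more records under the same rule would not remove the shift.

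**Working it through.** **The plan's own figures.** The protocol gives no figure for visit compliance or its bias. Its precision figures in section 9.5.2 come from n = p(1−p)z²/e² with p = 0.5 and z = 1.96:

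- e = 0.05 gives 384.1 (the protocol states 384).
- e = 0.10 gives 96.04, rounded up to 97 (the protocol states 97).
- The half-width is 9.8 points at n = 100 and 13.9 points at n = 50.

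These are the yardstick for the bias.

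**Is partial reporting plausible?**

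- The targets imply a mean of 50/20 = 2.5 to 100/15 = 6.7 patients per physician, below the cap of 10.
- Section 9.4 puts each record at about 10 minutes, so ten records take about 100 minutes.
- For the first report the window runs from launch to 31 March 2019: about 29 months for Belgium and the Netherlands (1 November 2016) and nearly 35 for Ireland (2 May 2016). The eligible pool is then larger than in later years.
- Nothing in the protocol requires all eligible patients to be reported.

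**Illustrative inputs (assumed, not in the documents).** Half of a physician's eligible patients visit 4 times a year and half visit less often. The physician has 10 eligible patients and reports the 5 most recent.

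*One patient reported, large pool.* Selection is proportional to visit rate, so the share of frequent visitors is 0.5×4 / (0.5×4 + 0.5×1) = 0.80 for 4 versus 1. For 4 versus 2 it is 2/(2 + 1) = 0.67.

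*Five of ten, evenly spaced visits, exactly five patients of each kind.* All five frequent visitors were seen within the last 3 months. At 1 visit a year, each infrequent visitor was seen in those 3 months with probability 0.25. If J of them were, the five most recent are a random five of 5 + J patients, so the expected frequent share is E[5/(5+J)] with J ~ Binomial(5, 0.25):

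0.237×1 + 0.396×0.833 + 0.264×0.714 + 0.088×0.625 + 0.015×0.556 + 0.001×0.5 ≈ 0.82.

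For 4 versus 2, J ~ Binomial(5, 0.5) and the same sum is 0.68.

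*Other spacing and case mix.* Simulation with exponential gaps, or with each patient's type drawn at random, gives lower values. The ranges for 5 of 10 reported, against a true 50%, are:

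| Visits per year | Frequent visitors in sample |
|---|---|
| 4 versus 1 | about 70–82% |
| 4 versus 2 | about 61–68% |
| equal rates | 50% |
| any rates, all eligible patients reported | 50% |

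*A different true value.* With true compliance of 60%, the 5 most recent reported and exponential gaps:

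| Visits per year | 7 eligible | 10 eligible | 20 eligible | 50 eligible |
|---|---|---|---|---|
| 4 versus 3 | 63% | 64% | 66% | 67% |
| 4 versus 2 | 67% | 70% | 73% | 74% |

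So the bias ranges from a few points to more than the 10-point precision target, depending on inputs that nobody has.

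**Would weighting repair it?** Weighting each patient by the inverse of visit frequency assumes that selection is proportional to visit rate. That fails when most eligible patients are reported. With 12 eligible (six of each kind, 4 versus 1) and 10 reported, nearly all six frequent visitors are in the sample, so the raw share is about 59–60%. The weighted share is 6×0.25 / (6×0.25 + 4×1) = 1.5/5.5 = 27% (26–27% across visit patterns), against a true 50%.

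**The case against.** The strongest reply is that the bias may not arise. Section 9.5.1 speaks of a low prescribing base and section 9.5.2 of very low patient numbers, and up to 10 patients may be reported, so many physicians may report everyone. That stands, and it is why the point is conditional. But the protocol neither asks for complete reporting nor collects the figure that would show it.

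A second reply is that selection follows the current visit rate while the outcome is first-year visits, so the link is indirect for patients past their first year. That stands too: the examples treat the two as the same, and a weaker link means a smaller bias. A third is that the knowledge criterion in section 9.7.3 cannot be affected by patient selection. That is correct, and the point is limited to the descriptive visit results.

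A reader might go further in three ways that the documents do not support:

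- *That compliance will certainly be overstated.* The bias is zero under complete reporting. Recency selection can also bring in recently started patients. If these were scored against a full year, measured compliance would fall.
- *That unrecorded weight, blood pressure and heart rate are dropped as missing at random.* The protocol does say that assessment of "blood pressure, weight and heart rate is required before initiation and during treatment", that the survey collects "frequency of monitoring and weight, blood pressure, heart rate if information is available", and that "Missing values are expected to be few and distributed at random". But the last is a general expectation. Section 9.7.3 rules out imputation and promises a description of missing data for each outcome; it does not say that blanks leave the denominator. Sections 9.3, 9.7.1 and 9.7.3 refer definitions and evaluation rules to the SAP, which is not at hand. A blank may also be a value that was taken but not entered.
- *That patients with under 12 months of treatment are mishandled.* How they are scored is likewise for the SAP, and the direction of any effect is open.

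**Conclusion.** The point holds for patient selection. The protocol fixes selection by most recent visit while visit frequency is part of the secondary objective. First-year visit compliance is therefore likely to be overstated wherever a physician reports fewer patients than are eligible. The illustrative 61–82% against a true 50% rests on assumed visit rates, 10 eligible patients with 5 reported, and current visit rate standing in for first-year visits. The true size could be zero or could exceed the plan's 10-point precision target. What can be said without assumptions is that the protocol does not acknowledge this bias, and that its planned variables would not reveal whether it occurred. Scoring of unrecorded measurements and short treatment are not findings here.

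**What to change.** - Add one question to the physician part of the questionnaire: the number N of eligible patients in the window.
- In sections 4.5, 9.2, 9.4 and 9.7.1, replace the recency rule. If N is 10 or fewer, request all eligible patients. If N exceeds 10, select up to 10 by a rule unrelated to visit recency, for example at random from the physician's list of eligible patients.
- Report the ratio of reported to eligible patients for each country and year.
- Where recency selection remains, name it as a limitation in section 9.9, with its likely direction.
- Do not rely on inverse-visit-frequency weighting as a repair, since it can over-correct badly.
- As a small clarification in section 9.7.3, do not apply the general missing-at-random expectation to monitoring measurements, and show not recorded as its own category.

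The cost is one extra question, slightly more record work for each physician (about 10 minutes per additional record by the protocol's own estimate), and a short wording change. The cap of 10 is unchanged. If caseloads are as small as the protocol expects, the extra burden is slight.

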9.5 STUDY SIZE

9.5.1 **Sampling plan**

Per country and year, the target is to collect data from 50 to 100 patients, who have been prescribed Intuniv[®] at least once during the study period, provided by representative physicians qualified to treat patients with ADHD. It is planned to annually recruit 15 to 20 prescribers of Intuniv[®] per country who will be requested to complete, if possible, 1 to 10 medical record extracts.

A random sampling plan will be developed. Prescribers will be sampled among the lists of paediatricians, GPs, neurologists and psychiatrists.

Due to the low prescribing base, no quotas by physician types will be set. As many patient medical records (anticipated maximum: 100 records per country) from as many prescribing physicians who are willing to participate will be collected.

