- completed the survey and sent it back to IQVIA Medical Radar,
- been reached out by phone or have opened their email (if the score is technically available in their country)
- refused to participate

Moreover, a physician will be considered as unreachable if he/she has been contacted at least 3 times without any answer.

For each physician of the sample file, the number of contacts, and the date and time when he/she completed the web questionnaire will be recorded. The recruitments in each country will be stopped when the target is reached.

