9.7 DATA ANALYSIS

9.7.1 General statistical consideration

The statistical analysis will be conducted using the SAS® software (like SAS 9.3) on WindowsTM (SAS Institute, North Carolina, USA).

A detailed statistical analysis plan (SAP), that could support independent replication of the study results, will be agreed on prior to the start of the analysis. Table shells, exact definitions of all variables (e.g. details on the calculation of average daily dose), the categories of variables to appear in the tables (e.g. age), and subgroup analyses of patients will be defined in the SAP.

The statistical results of the five countries will be presented annually in the same report. Results will be presented by country. Due to the low sample size no stratification by specialty is planned.

All the analysis will be descriptive in nature and no statistical comparison will be done in this study.

The survey will be performed once per year for four years. Physicians will always be asked annually to provide information on the last patient they saw who they had prescribed Intuniv[®] to: for the first report patients for who they had prescribed Intuniv[®] since launch; for later reports the most recent patients who they had seen for who they had prescribed Intuniv[®] to within the previous 12 months period (patients' selection window), regardless whether the patient had received an Intuniv[®] prescription at his/ her last visit. The observation period for the first report will be the country-specific launch date to 31 March 2019; for consecutive reports – until 31 March of the respective study year. The last survey will cover the period until 31 March 2022.

9.7.2 Representativeness of participating physicians- Analysis of non-participation or refusal to participate rate

As often required by the Authorities, the following different cases of total non-response will be distinguished and analyzed:

- Targeted physicians: Physicians reached to whom an email or mail has been sent, or have been called.
- Contacted physicians: Physicians who have been reached out by phone or have opened their email (if the score is technically available in their country).
- Physicians who agreed to participate: Physicians willing to participate in the survey (e.g. by phone or by clicking on the link provided in the recruitment email).
- Physicians with complete questionnaire: Physicians who actually completed the questionnaire until its end.

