9.9.2 Limits inherent to web-surveys

The questionnaire includes general questions followed by specific ones. As the physicians may understand the right answer in subsequent questions, it would not be possible to go back in the questionnaire and edit answers in former questions.

In such surveys, the generalisation and external validity of the results is restricted to physicians who have an active email address and willing (and able) to answer a

questionnaire online. These physicians may not be fully representative of the whole targeted population (18).

Among non-response bias, targeted physicians may also have activated filters in their mailbox in order to block spams and unsolicited emails. They may not even see the invitation to participate in the survey if a very strict degree of message filtering is set. Having multiple email addresses could also be a critical situation. If the one used is not the primary address, or if the physicians do not check their email box frequently, they will not receive the invitation during the recruitment period. This is one of the reasons why the physicians will also be contacted by phone.

Moreover, web-surveys may promote social desirability bias which refers to the tendency of physicians to give socially desirable/expected responses instead of choosing those reflecting their current knowledge or behavior, e.g. physicians can copy-paste information collected online instead of giving their own opinions (18).

Social desirability can affect the validity of survey research findings, but the use of prepopulated items in the questionnaire could/tends to reduce this bias (19).

The access to the web-questionnaire interface will be strictly limited to the invited participants, with the possibility to participate only once and a traceability system. Thus stakeholder bias (multiple answers of people who have a personal interest in survey results and/or who incite peers to fulfill the survey in order to influence the results) or unverified respondents (when it is not possible to verify who responds) are not applicable.

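### Section 9.2 does not prevent repeat physicians and 9.7.3 does not separate them, so the 2020–2022 verdicts on the educational material may be inflated by earlier exposure to the survey

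*Protocol*

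**What the plan says.** **Recruitment.** Protocol 9.7.1: "The survey will be performed once per year for four years". Section 9.2: "Recruitment of physicians will be done at random for each annual survey, with the aim to avoid having the same physicians in each survey". The next sentence allows for failure of that aim: "However, overlaps within the groups of physicians are still possible". No exclusion, cap or order of priority for earlier participants is stated.

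**Size of the pool.** Section 9.5.1: "It is planned to annually recruit 15 to 20 prescribers of Intuniv" per country. The same section says: "Due to the low prescribing base, no quotas by physician types will be set". The number of prescribers is not given.

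**Success rule.** Under 9.7.3 the material counts as effective if at least 80% of physicians answer at least 75% of the knowledge questions (A2 to A5) correctly. "In the main analysis all questionnaires will be evaluated"; the only subgroup is physicians who report having received the material (A7).

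**Cueing.** Section 9.9.2 blocks going back in the questionnaire and gives the reason: "As the physicians may understand the right answer in subsequent questions". It also says that an invited physician can take part only once, without saying whether that means per survey or over all four.

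**Records.** Section 9.6.1: "For each physician of the sample file, the number of contacts, and the date and time when he/she completed the web questionnaire will be recorded". Section 10.3.2 gives each physician a personalised login.

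**The concern.** A fresh random draw does not keep earlier participants out. In a small pool, repeats are what such a draw tends to produce. A physician who took part in an earlier round has already met the scored items, provided they stay the same, and may do better on them for a reason unrelated to the educational material. The protocol recognises that its questions can cue answers, but guards against this only within one sitting.

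The verdict serves the secondary objective and goes to EMA every year (section 12). If a later report declares the material effective, a reader cannot tell from the planned output whether repeat participants were few or many, or whether first-time participants alone would have met the rule. The A7 subgroup does not help, because receipt of the material and earlier participation are different things.

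**Working it through.** The protocol gives no figure for overlap. Its only computed sample sizes (97 and 384 in 9.5.2) concern patients; they reproduce (0.25 × 1.96² / 0.10² = 96.04 and 0.25 × 1.96² / 0.05² = 384.1) but do not bear on this point.

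**Inputs from the protocol:** n = 15 to 20 physicians per country and year; four rounds; an 80% threshold. **Assumed:** N willing prescribers per country, constant over time; independent draws each year; the pass rates below.

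**Step 1: share who took part before.** With f = n/N, the expected share is f in year 2, 1 − (1 − f)² in year 3 and 1 − (1 − f)³ in year 4. For example, n = 20 and N = 100 give 1 − 0.8³ = 0.488 in year 4.

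**Step 2: expected pass rate.** If first-time participants pass at 70% and repeat participants at 90%, a repeat share s gives 0.70 + 0.20s. This reaches 0.80 only when s ≥ 0.10/0.20 = 0.50.

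| N | Year 2 | Year 3 | Year 4 | Expected pass rate, year 4 |
|---|---|---|---|---|
| 50 | 30–40% | 51–64% | 66–78% | 83.1–85.7% |
| 100 | 15–20% | 28–36% | 39–49% | 77.7–79.8% |
| 200 | 8–10% | 14–19% | 21–27% | 74.2–75.4% |

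Of these three pool sizes, only N = 50 crosses the threshold in year 4. N = 100 falls just short even with 20 physicians (0.70 + 0.20 × 0.488 = 0.798).

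**Step 3: other pass rates.** The repeat share needed is (0.80 − p₁)/(p₂ − p₁), with p₁ for first-time and p₂ for repeat participants: 25% for 75% and 95%; 40% for 70% and 95%; 67% for 70% and 85%.

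**Step 4: chance of an effective verdict.** This is the exact probability for the sum of two binomials, with a first-time pass rate of 70%, repeats passing at 80% to 95%, and n held fixed. The rule needs 16 of 20 in one country, or 64 of 80 if four countries are pooled. The protocol does not say which applies.

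| Repeat share | n = 20 | n = 80 |
|---|---|---|
| none | 0.24 | 0.03 |
| 10% | 0.27–0.32 | 0.05–0.08 |
| 25% | 0.32–0.46 | 0.08–0.25 |
| 50% | 0.41–0.74 | 0.18–0.79 |

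The effect is small at 10% repeats and large at 50%.

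**The case against.** The strongest case against is that every quantity driving the effect is assumed. The protocol does not show that overlap will be material, that physicians retain answers for a year, that correct answers are fed back, or that the questionnaire stays unchanged. Section 9.9.2 speaks of later questions cueing earlier ones in one sitting, not of lasting learning. The overlap is disclosed, together with an aim to avoid it that the independent-draw model ignores. The sentence on evaluating all questionnaires is there to contrast with the A7 subgroup and is not a decision about repeat participants. All analysis is descriptive, and no year-on-year comparison is planned. Section 9.7.3 refers to the SAP, which is not at hand, for more detail on evaluating effectiveness.

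Most of this stands and limits the conclusion. A reader might infer that the later verdicts do measure learning from the survey, or that a rise towards 80% over the four reports would be produced by it. The documents support neither; they show only that the possibility is open. A reader might also infer that the 80% rule should rest on first-time participants alone. That does not follow either: at N = 50 and n = 20 only 20 × 0.6³ ≈ 4 physicians per country would be left in year 4, too few for an 80% rule.

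What does not stand is leaving everything to the SAP. Recruitment and the main analysis set are fixed in the protocol, and a split in the SAP would still need earlier participation to be identified from the contractor's records during fieldwork.

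**Conclusion.** The concern holds in a limited form. The protocol states an aim of avoiding repeat physicians but gives no means that achieves it in a low prescribing base, and its effectiveness analysis does not separate those who have seen the survey before. The 2020–2022 verdicts may be inflated by an unknown amount; the 2019 verdict cannot be. Depending on the assumed pool, the year-4 repeat share runs from about a fifth (N = 200) to over three quarters (N = 50), before any success in avoiding repeats. Whether that changes a verdict depends on an assumed learning gain: at 70% and 90%, repeats must be at least half of the sample. This calls for an inexpensive safeguard and is not evidence that any verdict will be wrong. Separately, the single-participation statement in 9.9.2 conflicts with 9.2 if it covers all four rounds, and gives no protection between rounds if it does not.

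**What to change.** - **Section 9.2:** have the survey contractor flag earlier participation from its own contact and login records, with the linking records kept from the sponsor. Within the random order, invite physicians who have not yet taken part first.
- **Section 9.7.3:** keep all questionnaires as the main analysis. For 2020–2022, report the number of repeat participants and show the 80% result separately for first-time and repeat participants as a sensitivity analysis. Attach a caution to the verdict if the combined and first-time results disagree.
- **Section 9.9.2:** state whether single participation applies per survey or over all surveys, and reconcile it with 9.2.

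**Cost.** The contact file must be linked across years, which the protocol does not now state, and the draw is no longer purely random. First-time denominators may be small in later years. Inviting new physicians first can avoid repeats only if a country has at least 4 × 15 = 60 to 4 × 20 = 80 willing prescribers over the four rounds; in a smaller fixed pool it delays them. At N = 50 and n = 20, for example, new physicians run out during year 3 (20 + 20 + 10), and year 4 would consist of repeats. The first-time row would then be empty, and the report should say so. Patient-level data from repeat physicians are not affected.
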